## 4.4.1 **Prohibited Therapy**

Drugs known to transfer to the breastmilk and with established or potential deleterious effects for the infant, including but not limited to aspirin (risk of Reye's syndrome), tetracyclines or fluoroquinolones are not permitted. A more detailed, though not comprehensive, list can be found in Appendix 2.

No formal drug-drug interaction studies have been conducted with ocrelizumab, as no drug-drug interactions are expected via the cytochromes P450, other metabolizing enzymes or transporters.

Ocrelizumab is a monotherapy and has not been studied in combination with other DMTs. As with other immunomodulatory therapies, exercise caution when initiating ocrelizumab after an immunosuppressive therapy, and when initiating another therapy after ocrelizumab, taking into consideration the potential for overlapping pharmacodynamic effects.

Immunosuppressants, lymphocyte-depleting agents, or lymphocyte-trafficking blockers should NOT be administered while the woman is B-cell depleted.

More information is available in Section 4.1.2 and the ocrelizumab labeling (USPI; SmPC).

#### 4.5 STUDY ASSESSMENTS

The schedule of activities to be performed during the study is provided in Appendix 1. All activities should be performed and documented for each mother or infant.

# 4.5.1 Informed Consent Forms and Screening Log

Written informed consent for participation in the study must be obtained before performing any study-related procedures (including screening evaluations). ICFs for enrolled women and their infants and for women who are not subsequently enrolled will be maintained at the study site. Where applicable, the written ICF with respect to the infant is also signed and dated by the holder of parental rights as designated by the maternal subject.

All screening evaluations must be completed and reviewed to confirm that women meet the eligibility criteria before enrolment. The investigator will maintain a detailed record of all participants screened and document eligibility or record reasons for screening failure, as applicable. Reasons for screening failure will also be captured by the sites in the eCRF.

## 4.5.2 Mother's Assessments

# 4.5.2.1 Demographics, Medical and MS History, and Disease Characteristics

Women's demographics (age, self-reported ethnicity, and level of education) and relevant medical history, including clinically significant diseases, surgeries/procedures, vaccination history, smoking history and alcohol intake will be recorded during the screening period. In addition, all medications (e.g., prescription drugs, over-the-counter drugs, vaccines, herbal or homeopathic remedies, nutritional supplements) used by the woman within 6 weeks prior to the baseline visit will be recorded. Clinically significant diseases and/or surgeries and concomitant medication should also be recorded throughout the study if available.

## Obstetric history:

History of previous pregnancies

## MS disease history:

- Date of MS symptom onset and MS diagnosis
- Disease status (as available): EDSS and number of relapses up to 1 year before the LMP
- History of previous DMTs (prior to and during pregnancy): number of DMTs ever used, last DMT before ocrelizumab
- Treatment history with ocrelizumab (to be collected only in women who received commercial ocrelizumab prior to enrolment): Documentation of start of ocrelizumab therapy and date and dose of last ocrelizumab infusion prior to enrolment.

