# 4.1.1 Inclusion Criteria

The following criteria must be met for study entry:

- An Informed Consent Form (ICF) for participation of the maternal subject and her infant (for collection of blood, infant demographic and adverse event data) is signed and dated by the subject. Where applicable, the written ICF with respect to the infant is also signed and dated by the holder of parental rights as designated by the maternal subject
- Woman is able and willing to comply with the study protocol, according to the judgment of the investigator, in particular:
  - Woman is willing to breastfeed (either exclusively, or with formula supplementation) for at least 60 days after the first postpartum ocrelizumab infusion (this decision is to be taken prior to and independent from study participation)
  - Woman is willing to provide breastmilk samples before and after their first and, if applicable, second postpartum ocrelizumab infusion
    - Note: Exposure to ocrelizumab includes administration of an initial split dose of two 300 mg infusions (in 250 mL 0.9% sodium chloride) separated by 14 days for women initiating treatment with ocrelizumab, or a single 600 mg infusion (in 500 mL 0.9% sodium chloride) for women already on treatment with ocrelizumab.
- Woman is between 18 and 40 years of age at screening
- Woman has a diagnosis of MS or CIS (in line with the locally approved indications)
- Woman has delivered a healthy term singleton infant (≥37 weeks gestation)
- Infant is between 2–24 weeks of age at the time of the mother's first postpartum dose of ocrelizumab
- For women who received commercial ocrelizumab (OCREVUS) before enrolment: documentation that last exposure ocrelizumab occurred more than 3 months before the LMP (i.e., excluded a potential fetal exposure) and was given at the approved dose of 2×300 mg or 1×600 mg

- Woman agrees to use acceptable contraceptive methods or alternative methods during the study as described below and, if applicable, upon study treatment discontinuation, as defined by the local prescribing information (see Section 4.6.1).

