#### Exclusions related to the mother

- Hypersensitivity to ocrelizumab or to any of its excipients
- Woman received last dose of ocrelizumab < 3 months before the LMP or during pregnancy (i.e., there was a potential fetal exposure to ocrelizumab)
- Active infections (note: the woman may be included once the infection is treated and is resolved; women with bilateral mastitis infection should not have samples collected until the infection is completely resolved)
- Prior or current history of primary or secondary immunodeficiency, or woman in an otherwise severely immunocompromised state. Woman may be re-screened and included if condition resolves
- Woman with known active malignancies, or being actively monitored for recurrence
  of malignancy including solid tumors and hematological malignancies (except basal
  cell and in situ squamous cell carcinomas of the skin). Women with high risk of
  breast malignancies undergoing prophylactic treatment with drugs such as
  tamoxifen are excluded

- Woman has history of breast implants, breast augmentation, breast reduction surgery or mastectomy
- Woman has prior or current history of chronic alcohol abuse or drug abuse
- Woman has any medical, obstetrical or psychiatric condition that, in the opinion of the investigator, would compromise the woman's ability to participate in this study
- Treatment with a DMT for CIS or MS during pregnancy and/or first weeks postpartum, with the exception of formulations of interferon-beta, glatiramer acetate or pulsed corticosteroids
- Drugs known to transfer to the breastmilk and with established or potential deleterious effects for the infant, including but not limited to aspirin (risk of Reye's syndrome), tetracyclines or fluoroquinolones. A more detailed, though not comprehensive, list can be found in Appendix 2
- Treatment with any investigational agent within 6 months or five half-lives of the investigational drug (whichever is longer) prior to the LMP, unless the investigational agent is ocrelizumab administered > 3 months prior to the LMP in the context of a study or registry sponsored by Roche

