- Medical history includes clinically significant diseases, surgeries/procedures, smoking history, alcohol intake and all medications (e.g., prescription drugs, over-the-counter drugs, vaccines, herbal or homeopathic remedies, and nutritional supplements) used by the woman within 6 weeks prior to the baseline visit. Demographic data will include age, self-reported race/ethnicity, and level of education. Clinically significant diseases and/or surgeries and concomitant medication should also be recorded throughout the study. Information on vaccinations administered to the mother during the study will be collected under concomitant medications.
-  Documentation of start of ocrelizumab (OCREVUS) therapy and date and dose of last ocrelizumab infusion prior to enrolment. Ocrelizumab-related information to be collected only in women who received commercial ocrelizumab prior to enrolment.

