- Number of patients by the most recent DMT
- Reason for discontinuing most recent DMT
- Duration of the most recent DMT as continuous and categorical (≤6 months, >6 and ≤12 months, >12 and ≤24 months, >24 months)
- Time (months) from last DMT to LMP prior to study
- Time (months) from last DMT to first ocrelizumab prior to study

Multiple Sclerosis History - Prior Ocrelizumab Use

- Received ocrelizumab prior to the study (Yes, No)
- Duration (months) of ocrelizumab therapy prior to enrolment
- Duration of ocrelizumab therapy prior to enrolment (≤6 months, >6 and ≤12 months, >12 and ≤24 months, >24 months)
- Time (months) between last ocrelizumab infusion and the last menstrual period (LMP) (3 to ≤6 months, >6- to ≤9 months, >9 to ≤12 months, >12 months)
- Time (months) between delivery and first post-partum ocrelizumab infusion

Baseline Disease Characteristics

- Baseline EDSS continuous
- Baseline EDSS distribution: count and percent of patients corresponding to each observed score of EDSS at baseline
- For those who underwent neurological examination at baseline, any new clinically significant abnormalities since last exam (Yes, No)
- Type of abnormality for those with clinically significant abnormalities since last exam (disability progression independent of relapse, MS relapse, signs or symptoms suggestive of Progressive Multifocal Leukoencephalopathy, Other)

Obstetric and Gynecological History

- History of previous pregnancies (Yes/No)
- Number of previous pregnancies (1, 2, 3, 4, >4)
- Previous pregnancy outcome (Full term live birth, preterm live birth, spontaneous abortion, still birth, therapeutic abortion, elective abortion, ectopic pregnancy, unknown)
- History of obstetrical complications during previous pregnancies (Yes/No)

Medical History

Medical history of the mother will be summarized in the SAFM by SOC and PT. For each previous and concurrent medical history recorded medical history (MH), the term entered

by the investigator describing the event (the "reported term") will be assigned a standardized term (the "Preferred Term" [PT]) and assigned to a superclass term (the "System Organ Class" [SOC]) on the basis of the MedDRA World Health Organization (WHO) dictionary of terms.

Vaccination History

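### Women whose earlier ocrelizumab came only from a sponsor study are eligible, but the date and dose of their last infusion are not a specified data item, although two SAP analyses need the date

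*Protocol*

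**What the plan says.** **Eligibility.** The maternal exclusions in Protocol 4.1.2 bar investigational agents taken within 6 months or five half-lives before the LMP, whichever is longer, unless the "investigational agent is ocrelizumab administered > 3 months prior to the LMP in the context of a study or registry sponsored by Roche". No dose condition is attached. A separate item in the same list excludes any woman whose last ocrelizumab fell less than 3 months before the LMP or during pregnancy, however it was supplied.

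**Documentation and dose.** The inclusion criterion in 4.1.1 reads "For women who received commercial ocrelizumab (OCREVUS) before enrolment: documentation that last exposure ocrelizumab occurred more than 3 months before the LMP". The same sentence adds that the exposure "was given at the approved dose of 2×300 mg or 1×600 mg". Both parts hang on the opening words about commercial product.

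**Data collection.** In Section 4.5.2.1, under MS disease history: "Treatment history with ocrelizumab (to be collected only in women who received commercial ocrelizumab prior to enrolment". What is collected is "Documentation of start of ocrelizumab therapy and date and dose of last ocrelizumab infusion prior to enrolment". Appendix 1, footnote g, repeats the limit: "Ocrelizumab-related information to be collected only in women who received commercial ocrelizumab prior to enrolment". These restrictions are the same in version 3 and version 4 (United States), and SAP Appendix 2 reproduces the footnote.

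**Analysis.** SAP 4.3.1 lists "Received ocrelizumab prior to the study (Yes, No", the duration of prior ocrelizumab, and the time from last infusion to LMP in bands from 3 months to over 12 months. SAP 4.6.3 plans relapse counts among women whose last ocrelizumab was within 12 months before the LMP, one of them in the window 6 to 9 months after that dose. Neither section is limited to commercial product.

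**The concern.** The protocol admits a group on the strength of one interval, last infusion to LMP, and then tells sites to collect the date behind that interval only for a different group. This is an express restriction, not an omission that a site might fill by default.

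The interval matters because Section 3.3.2 gives fetal exposure as a possible confounder of the infant B-cell results, and B-cell level is a co-primary endpoint. The schedule has no infant lymphocyte sample before Day 30. A low count therefore cannot be compared with a value from before the mother's infusion. The recorded interval is the main evidence in the study data that an infant was not exposed in utero. The SAP also needs the date directly for two outputs.

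**Working it through.** The plan gives no figure for this point, so the check is a comparison of provisions for two kinds of prior user.

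| Provision | Prior commercial ocrelizumab | Prior ocrelizumab in a sponsor study only |
|---|---|---|
| Exclusion if last dose under 3 months before LMP, or in pregnancy (4.1.2) | applies | applies |
| Documentation of the interval (4.1.1) | required | not required |
| Prior-dose condition (4.1.1) | applies | not stated |
| Start, last date and last dose collected (4.5.2.1, footnote g) | yes | excluded by the wording |
| Prior use, duration, interval to LMP (SAP 4.3.1) | planned | planned |
| 12-month relapse subset (SAP 4.6.3) | planned | planned |

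The third and fourth rows need reconciling with the waiver in 4.1.2. The fourth also conflicts with the last two.

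**Who falls in the right-hand column.** A woman who ever had commercial product is covered by 4.5.2.1, including a registry patient on marketed drug. The gap is confined to women whose prior ocrelizumab was never commercial. With the average half-life of 26 days in Section 3.3.2, five half-lives are 5 × 26 = 130 days, which is less than 6 months. The investigational-agent exclusion therefore looks back 6 months, and the waiver opens the part of that period more than 3 months before the LMP. Women with study ocrelizumab further back are eligible without the waiver, and the collection limit applies to them too.

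**Whether another specified item supplies the date.**

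- Prior medication (4.5.2.1) reaches back 6 weeks before baseline. With a last dose more than 3 months (about 13 weeks) before the LMP, at least 37 weeks of gestation (counted from the LMP) and at least 2 weeks postpartum, the last infusion lies at least 13 + 37 + 2 = 52 weeks before baseline.
- The DMT history asks for the number of DMTs and the last DMT before ocrelizumab, not for ocrelizumab's own dates.
- The screening record (4.5.1) must document eligibility, but names no date or dose field.

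**What follows for the SAP.** For a woman in the right-hand column, time from last infusion to LMP, membership of the 12-month subset and the 6-to-9-month relapse window all require the last-infusion date. Duration of prior therapy requires the start date. The protocol specifies no source for either, and the SAP has no rule for these women.

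**The case against.** The best defence is that the safeguard itself is intact. The under-3-months exclusion does not depend on source, the study-drug waiver itself requires more than 3 months, and Section 4.5.1 requires eligibility to be reviewed and documented before enrolment. A site cannot do that without establishing when the last dose was given. This stands in full. A reader might infer that the 3-month rule goes unchecked for these women, and the documents do not support that. What is missing is a specified data item, not the rule.

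Second, other data bear on residual maternal drug: milk is assayed before the first infusion and maternal CD19+ cells are counted at screening. Neither depends on product source. But neither dates the last dose, and the pre-infusion milk sample comes at least 52 weeks after a permissible last dose (arithmetic above), so it says little about levels near conception.

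Third, SAP 4.3.1 also plans the most recent DMT and the time from last DMT to LMP, so DMT dates may exist in the case report form, which is not among the documents. That is a possible route to the date. It is not a specified one, and the express limit in 4.5.2.1 and footnote g points the other way. For the same reason, an inference that these women would be coded as having no prior ocrelizumab goes too far: the SAP does not name its source field.

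Fourth, the group may be empty. That is fair, and it limits the priority.

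**Conclusion.** The inconsistency holds in both protocol versions. If the text is followed, prior-ocrelizumab summaries and the 12-month relapse subset would be incomplete for women treated only in a sponsor study, and absence of fetal exposure could not be examined for them from the study data.

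No numerical effect on a co-primary endpoint can be given. The documents do not state how many such women are expected among the planned 10 or more, and the number may be small or zero. It is tempting to size the point with the half-lives in Section 3.3.2, 26 days on average and 53 days at the longest. That would describe any woman dosed just over 3 months before the LMP, including a fully documented commercial patient, so it would question the threshold rather than this gap. Nor do the documents suggest that prior study doses were larger: Section 1.2 gives 600 mg for the Phase III trials. A reader might also infer that an infant's low count could be wrongly attributed to lactation because of this gap. That would need an ineligible woman to pass an exclusion that binds her, and nothing in the documents indicates that.

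The conclusion assumes that the case report form follows the protocol wording. It is a low-cost correction and does not invalidate the design.

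**What to change.** 1. In Section 4.5.2.1 and Appendix 1 footnote g (versions 3 and 4), and in SAP Appendix 2, collect the date and dose of the last infusion for any prior ocrelizumab, commercial or investigational. Collect the start of therapy on the same basis, because the SAP duration summary uses it.
2. In SAP 4.3.1 and 4.6.3, derive prior use, interval to LMP and the 12-month subset from both sources.
3. The sponsor should reconcile 4.1.1 with 4.1.2 on what must be documented for women with study ocrelizumab, and should state whether the prior-dose condition applies to them. Simply deleting the word commercial from 4.1.1 would extend the dose condition as well, because one sentence carries both. That rule is for the sponsor to settle.

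For women already enrolled, a site query or the sponsor's own study records could supply the values. The cost is wording in a few places, any matching change to the case report form, and a few extra history fields.

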# 4.5.2.2 Physical Examinations and Related Assessments

A complete physical examination in participating women should include an evaluation of head, eye, ear, nose, and throat, cardiovascular, dermatological, musculoskeletal, respiratory, and gastrointestinal systems, as well as vital signs (see following section). To reduce the burden of visits on the mothers, results from physical examinations done as part of routine care at the woman's HCP (obstetrician/gynecologist, pediatrician and/or neurologist of referred woman) may be used. Any abnormality identified at baseline should be recorded on the General Medical History and Baseline Conditions eCRF. Changes from baseline abnormalities should be recorded in patient notes. New or worsened clinically significant abnormalities not related to MS should be recorded as adverse events on the Adverse Event eCRF. Height will be recorded at screening only.

The following assessments will also be conducted: neurological examination (see Section 4.5.2.4), relapse description and EDSS (see Section 4.5.2.6).

See Appendix 1 (Schedule of Assessments) for the timing of assessments.

## 4.5.2.3 Vital Signs

Vital signs may be measured, in particular throughout the infusion procedure as per the label, and may include measurements of heart rate, systolic and diastolic blood pressures, and temperature. If these measurements are performed as per clinical practice and are available, any abnormalities should be recorded on the General Medical History and Baseline Conditions eCRF. At subsequent visits, new or worsened clinically significant abnormalities should be recorded on the Adverse Event section of the eCRF (as presented in Section 5.1.2).

## 4.5.2.4 Neurological Examinations

A neurological examination will be performed at baseline, early study discontinuation as well as at unscheduled visits if applicable, to distinguish relapse in MS from another neurological (non-MS) disorder. To reduce the burden of visits on the mothers, results from neurological examinations done as part of routine care may be used. For women referred to the investigator, results from routine visits at the woman's neurologist may be used. In the presence of newly identified or worsening neurological symptoms at any given time in the study, a neurological evaluation should be scheduled promptly.

As infection is a potentially serious complication of B-cell-depleting therapy, investigators will also screen women for signs and symptoms of any CNS infections, and specifically progressive multifocal leukoencephalopathy (PML), by evaluating neurological deficits localized to the cerebral cortex, such as cortical symptoms/signs, behavioral and neuropsychological alteration, retrochiasmal visual defects, hemiparesis, cerebellar symptoms/signs (e.g., gait abnormalities, limb incoordination). Women with suspected PML should be withheld from ocrelizumab treatment until PML is ruled out by complete clinical evaluation and appropriate diagnostic testing. A woman with confirmed PML should be withdrawn from the study. PML should be reported as a serious adverse event (with all available information) with immediate notification of the Medical Monitor. Refer to Appendix 3 for guidance for diagnosis of PML.

## 4.5.2.5 Assessment of Relapses

Potential relapses should be recorded throughout the treatment period. See Appendix 1 (Schedule of Assessments) for the timing of these assessments.

All new or worsening neurological events consistent with MS representing a "clinical relapse" are to be reported on the dedicated "MS relapse" form. A clinical relapse is defined as a monophasic clinical episode with patient-reported symptoms and objective findings typical of MS, reflecting a focal or multifocal inflammatory demyelinating event in the CNS, developing acutely or sub-acutely, with a duration of at least 24 hours, with or without recovery, and in the absence of fever or infection (Thompson et al. 2018). MS relapses should not be reported as an adverse event, unless they are serious.

It is recommended that women with new neurological symptoms suggestive of a relapse have an EDSS/Functional Systems Score (FSS) assessment performed as soon as

possible, ideally within 7 days of the onset of symptoms. However, it is not mandatory to perform an EDSS assessment in case of a suspected relapse.

